EVALUATION PROTOCOL

Evaluation of the Trauma Informed Schools UK Training and Implementation (TISUK): A cluster randomised controlled trial

Ipsos UK, The University of Kent, TONIC

Principal investigator: [name], [name],
[name], [name], [name]
[name]

Evaluation of the Trauma Informed Schools UK Training and Implementation (TISUK): A cluster randomised controlled trial

Evaluation protocol

IPSOS UK, TONIC and the University of Kent

Principal investigators: [name], [name], [name], [name], [name]

Project title¹	Evaluation of the Trauma Informed Schools UK Training and Implementation (TISUK): A cluster randomised controlled trial
Developer (Institution)	TISUK
Evaluator (Institution)	Ipsos UK, The University of Kent, TONIC
Principal investigator(s)	[name], [name], [name], [name], [name]
Protocol author(s)	[name], [name], [name]
Trial design	Two-armed cluster randomised controlled trial with random allocation at the school level
Trial type	Efficacy
Evaluation setting	School
Target group	Children and young people (CYP) in Year 8

¹ Please make sure the title matches that in the header and that it is identified as a randomised trial as per the CONSORT requirements (CONSORT 1a).

Number of participants	100 schools and 16,000 Year 8 pupils (with 1,100 receiving targeted support)
Primary outcome and data source	Externalising behaviour: SDQ – combined conduct and hyperactivity scores (Survey)
Secondary outcome and data source	
(CYP) Internalising behaviour: SDQ – combined emotional regulation and peer problems (Survey)
 
(CYP) Prosocial behaviour: SDQ – Prosocial behaviour (Survey)
 
(CYP) Total difficulties: SDQ – combined emotional regulation, hyperactivity, conduct, and peer problems (Survey)
 
(CYP) Non-psychotic psychological distress: General Health Questionnaire (GHQ12) (Survey)
 
(CYP) Well-being: Short Warwick Edinburgh Mental Well-being Scale (Survey)
 
(CYP) Sense of connectedness: School Connectedness Scale (Survey)
 
(CYP) Percentage of exclusions & suspensions: administrative records
 
(CYP) School attendance: administrative records
 
(School staff) Attitudes related to TIC: Attitudes Related to Trauma Informed Care (ARTIC) (Survey)
 
(School staff) Well-being: Short Warwick Edinburgh Mental Well-being Scale (Survey)
 
(School) Staff retention: administrative records
 
(School) Staff sickness: administrative records
 
(School) Percentage of exclusions & suspensions of CYP: administrative records

	(School) Percentage of school attendance of CYP: administrative records
--	--

Table of contents

Table of contents	3
Protocol version history	5
1. Study rationale, background and evidence for equipoise	5
2. Intervention	7
2.1. Who (recipients of the intervention)	8
2.2. What (physical or information materials used in the intervention)	8
2.3. What (procedures, activities and/or processes used in the intervention)	8
2.4. Who (intervention providers/implementers)	11
2.5. How (mode of delivery)	11
2.6. Where (location of the intervention)	11
2.7. When and how much (duration and dosage of the intervention)	12
2.8. Theory of change	12
3. Impact evaluation	14
3.1. Research questions (efficacy)	14
3.2. Design	17
Table 1 Trial design	20
3.3. Randomisation	23
3.4. Participants	25
3.5. Sample size calculations	26
Table 2 Impact of different pupil and school retention rates on sample size	27

Table 3 Impact of different pupil and school retention rates on MDES.....	28
Table 4 Sample size calculations.....	29
4. Outcome measures.....	30
Table 5 Primary and secondary outcomes.....	30
4.1. Analysis	36
Table 6 Statistical analysis by outcome and level.....	37
5. Implementation and process evaluation (IPE).....	39
5.1. Research questions (IPE).....	40
5.2. Research methods	40
Table 7 IPE methods overview.....	41
5.3. Analysis (IPE)	49
6. Cost data reporting and collecting.....	51
7. Diversity, equity and inclusion.....	51
8. Ethics and registration	52
9. Data protection.....	52
10. Stakeholders and interests	55
11. Risks	56
Table 8 Risks and mitigation measures.....	57
12. Timeline.....	61
Table 9 Timelines and milestones.....	61
13. References	63
14. Appendix 1: Theory of change	65
15. Appendix 2: QED initial study plan	66
Appendix - Table 1 QED design.....	66
Appendix - Table 2: Sample size calculations - QED	68

Appendix - Table 3 Impact of differential cluster size on the proportion of schools retained for the intervention group.....71

16. Appendix 3: Engagement tool74

Protocol version history

Version	Date	Reason for revision
1.2	July 2024	
 Updated the sections on fidelity, engagement, and compliance (see section 5)
1.1 [latest]	February 2024	
 Update to indicate that geographic location of school has been dropped from the stratification mechanism at randomisation stage (see section 3.3 for explanations) Updated to explain the timing of randomisation in two batches to accommodate fieldwork of baseline testing in schools (see section 3.3) Updated all the geographic region from where schools will be recruited (see section 2.6)
1.0 [original]	October 2024	

1. Study rationale, background and evidence for equipoise

Background of the problem

Numerous scientific studies have confirmed the severe impact of multiple adverse childhood experiences (ACEs) on children and young individuals. These distressing experiences increase the risk of developing mental health problems, behavioural issues, social difficulties, and learning disabilities, as well as contributing to poverty, long-term unemployment, self-harm, and engagement in violent and criminal activities (Baglivio, Wolff, DeLisi, & Jackowski, 2020; Felitti et al., 1998; Neil et al., 2022). This issue is particularly concerning in the UK, with over two million minors facing mental health difficulties, leading to more than 66,000 recorded referrals to Child and Adolescent Mental Health Services (CAMHS) in 2022. Shockingly, the End the Wait Campaign reported that 25% of these young individuals attempted suicide while

waiting for treatment, highlighting the dire state of waiting lists in many UK areas (Young Minds, 2023). ACEs have long-lasting effects and increase the risk of serious, violent, and chronic juvenile offending due to trauma-induced adverse changes in the brain and body, such as an overactive threat response system, abnormal hormonal axis functioning, impaired reward processing, and diminished executive functions in the frontal lobes (Blankenstein et al., 2022; McCrory et al., 2011; Van Voorhees & Scarpa, 2004).

In schools, traumatised children often display behavioural and relational issues, classified as conduct disorders or anti-social behaviour. Unfortunately, punitive measures and zero-tolerance policies used to address these behaviours worsen mental health problems instead of addressing their root causes. As stressed by (Le, Abdinasir, & Rainer, 2023) such approaches negatively affect traumatised children's well-being and fail to encourage positive behavioural changes. Consequently, these vulnerable children are often expelled from schools instead of receiving the necessary support to cope with their trauma, contributing to the school-to-prison pipeline phenomenon. For instance, research shows that a significant proportion of the 85,000 people in UK prisons were previously excluded from school during childhood (IPPR, 2017). The correlation between school disengagement, exclusion, and an increased risk of youth violence is emphasised by the Youth Safety Taskforce (Gill, Quilter-Pinner, & Swift, 2017). Hence, adopting alternative strategies to support this vulnerable student population is crucial for society.

TISUK's intervention

An alternative approach to dealing with children and young people (CYP) in a school setting who have suffered ACEs is a trauma-informed practice (TIP) framework. Previous research on TIP indicates that TIP training can immediately affect staff awareness and knowledge. Additionally, it appears to enhance positive interactions between young individuals and practitioners. However, initial findings propose that a comprehensive approach is necessary for substantial changes in practice – a pivotal factor in the TIP theory of change influencing child-level outcomes. This approach combines training with whole organisation strategies, involving senior leadership, training frontline practitioners, and creating a supportive environment that acknowledges and assists practitioners dealing with their own or vicarious trauma. Merely conducting training in isolation is unlikely to achieve the desired results (Molloy, 2022).

TISUK has developed a TIP framework with promising results. TISUK offers a comprehensive training package for schools, equipping all staff with insights into the neuroscience and psychology of psychological trauma and its impact on behaviour, learning, relationships, and mental health. They assist school leadership in fostering a mentally healthy culture by developing trauma-informed policies and practices.

Their approach is rooted in deep knowledge of emotionally healthy and unhealthy organisational environments (Høidal & Hanssen, 2022; Marmot & Brunner, 2005; McIntyre & Mazza, 2020; Sapolsky & Share, 2004) to address disaffection, feelings of undervaluation, isolation, anxiety, depression, and stress-related issues. TISUK also trains staff in creating supportive environments where individuals feel valued and seen, especially during times of stress, enhancing their ability to provide positive student experiences.

Preliminary evidence and rationale for equipoise

Over the last six years, TISUK has collaborated with over 5,000 educational professionals across the UK, including every school in Cornwall, through the HeadStart Kernow project funded by Big Lottery Fund. According to monitoring data collected by TISUK, the experience of schools implementing the TISUK approach suggests positive outcomes, including decreased fixed-term exclusions, suspensions, and incidents of physical restraint. Additionally, there has been an improvement in staff and student well-being, learner engagement, attainment, and attendance. Staff have reported that vulnerable CYP develop trusting relationships with emotionally available adults (EAAs), leading to transformative changes in their trauma recovery. Many school staff delegates have expressed that the training not only transformed their relationships with students at school but also improved their relationships with family members at home. This qualitative evidence suggests that schools could play a role in mitigating mental health disorders and behavioural issues among traumatised children and young individuals.

Furthermore, TISUK's comprehensive efforts align with the UK Government's Green Paper on Children and Young People's Mental Health. The Green Paper emphasizes the effectiveness of adequately trained and supported school staff, such as teachers, school nurses, counsellors, and teaching assistants (TAs), in dealing with mild to moderate mental health concerns. These concerns encompass issues like anxiety, conduct disorder, substance use disorders, and post-traumatic stress disorder (Department of Health and Social Care & Department for Education, 2018).

Despite the intervention showing promise and offering potential benefits, its effectiveness remains uncertain due to the limited availability of robust evidence supporting this approach. Consequently, this trial aims to address this gap and provide valuable insights.

2. Intervention

This section describes the intervention following the Template for Intervention Description and Replication (TIDieR)².

Brief name: Trauma Informed Schools UK Training and Implementation

2.1. Who (recipients of the intervention)

The intervention will be implemented across the whole school by improving school staff awareness of TIPs leading to changes in policies and practices that are consistent with TIP.

The whole-school intervention targets primarily school staff who are expected to implement institutional changes but also all CYP attending the school. The intervention encompasses headteachers/school leaders, staff directly working with vulnerable CYP, and the CYP themselves. The TISUK team is responsible for providing school staff with comprehensive training, including whole staff and senior leadership training, network consultancy, and reflective supervision training. Moreover, webinars for staff and students, along with specialized diploma practitioner training for selected teachers, will be facilitated by the TISUK team. A subgroup of more vulnerable CYP will receive extra and targeted support from these practitioner-trained school staff.

2.2. What (physical or information materials used in the intervention)

The intervention will make use of the following resources:

- 4 x Webinars with discussion guides and e-books
- Delegate Handbook (Diploma)
- ‘Helping teenagers talk about their lives’ cards
- Senior Lead Training e-book
- School wellbeing audit and staff wellbeing questionnaire
- Implementation checklist and RAG rating for network consultancy

2.3. What (procedures, activities and/or processes used in the intervention)

The intervention consists of six activities:

² Cochrane Collaboration and Training, C., 2022. Template for Intervention Description and Replication (TIDieR).

1. **Whole staff training:** The entire school staff, including support staff, administrators, and others, will participate in two 3-hour sessions. These sessions aim to provide staff with an overview of what constitutes trauma, its potential impact, ACEs, protective factors, the neuroscience of trauma, and relational approaches. The two sessions will be scheduled with a gap of 2-3 terms, strategically timed to address the decrease in momentum that typically occurs after the initial project launch. The sessions will be conducted virtually, potentially accommodating multiple schools in each training session. These sessions serve as the initial catalyst for staff members. They ignite interest and change attitudes to distressed and vulnerable CYP whilst outlining what is needed to implement a whole school approach. The whole school training lays the foundation for further development of staff understanding and skills as well as empowering each member of the school community to see that they have a role to play.
2. **Senior leadership training:** This training will involve approximately six members (5-7 depending on the size of the school) of the Senior Leadership Team (SLT) from each school. They will attend a 2-day training session focusing on the key elements of creating a trauma-informed and mentally healthy culture, through ethos, policy and practice. The training aims to increase understanding of the effects of trauma, develop skills and understanding to implement effective relational practice, procedure and interventions to break the cycle from ACEs to criminal behaviour and violence. Leadership will be equipped with the tools, materials and knowledge to evaluate and track TIP within their organisation. There is a focus on fostering psychologically safe and inclusive environments and delegates are asked to identify priorities for staff wellbeing and ensure access to EAAs for all. The training will be conducted in cohorts across the project schools, with SLT members from each school attending the training at different times, minimising the impact on the day-to-day running of the school.
3. **Network consultancy support:** Schools will be provided with three consultancy support meetings from an experienced educational consultant at TISUK with each one involving two to three schools. The purpose of this is to support school leaders to embed changes in culture, policy and practice; they will identify and overcome barriers to implementation within the unique context of their school, monitor the quality of provision and identify accurately priorities for improvement as well as opportunities for peer support and the sharing of best practice, ideas and resources.
4. **Diploma practitioner training:** Approximately six staff members (5-7 depending on size of school) will be chosen from each school to undergo a comprehensive 11-day Level 5 Diploma Practitioner Training. This training will be conducted over 5-6 months in 2-day blocks, with a final assessment to complete their accreditation. Delegates will be required to deliver a presentation on the implementation of their new knowledge and skills. TISUK recommend including at least one member from the SLT who has strategic

oversight and can oversee the organisation of resources and interventions and embed practice into policy. Other staff members are likely to be teachers, Special Educational Needs Co-ordinators (SENCOs), pastoral leads or TAs. The training aims to provide these individuals with a deeper understanding of trauma and its recovery process, equipping them with the skills, knowledge and understanding to respond effectively. It covers topics such as identifying protective factors and safety measures within the school culture, skill and knowledge development to provide targeted support to vulnerable children through individual or small group interventions, implementing strategies and approaches to support staff and fostering a trauma-informed school culture, as well as enhancing communication skills to promote and challenge the practices of others. Once trained, these practitioners assume the role of champions within the school; they provide support to students directly and enable them to reflect on painful life experiences. They also collaborate with the SLT to bring about cultural, policy, and practice changes within the school which includes updating and overseeing the school's referral process for vulnerable pupils and integrating TISUK measurement tools into this where appropriate. They receive mentoring throughout the process.

5. **Reflective supervision workshops:** Reflective Supervision is a supportive, respectful and purposeful process which is a vital component of a Trauma Informed School community. The aim of Reflective Supervision is for staff to feel supported enough to reflect with another and to gain further professional insight into work related interactions and patterns of behaviour or underlying emotional need. It is fundamentally concerned with how to best support practitioners, to best support the children with whom they work alongside. TISUK will offer Reflective Supervision training to two practitioners from each school who have completed the 11-day diploma training. These two practitioners will need to access external supervision themselves, but the training aims to equip them with the necessary skills to establish an effective, sustainable reflective supervision model for key staff across their setting.
6. **Webinar viewing for staff and CYP:** Schools will be given access to three webinars for staff and young people to view at a convenient time: 1) *The Neuroscience and Psychology of Relationships*, 2) *The Neuroscience and Psychology of Emotions* 3) *The Psychology of Gangs, Violence and County Lines from People Who Know*. Teachers will be asked to lead a discussion after each of these; guidance will be provided to staff on how to facilitate this. There will also be one webinar for all staff to view: *Conversations that Matter; from racial trauma and discrimination in schools and communities, to respecting and celebrating difference and diversity (policy & implementation)*.

Based on TISUK's previous experience, the project is expected to yield the following outcomes within the first 5-6 months:

- a. Staff: Increased knowledge, understanding and skills regarding the causes and impact of trauma and how relationship-based approaches can support when working with young people who have experienced past traumatic events. Staff respond to young people in ways that are stress reducing, promote connection and safety and enable CYP to make sense of their experiences.
- b. Schools: Enhanced staff support structures, changes in school policies and procedures to create a mentally healthy culture and the creation of psychologically safe environments. This should lead to improved mental health and well-being amongst staff and students and as a result reduced absence and increased engagement.
- c. Students: Heightened feelings of safety, improved relationships with EAAs, decreased exclusions, and enhanced attendance, engagement, and academic achievement. Furthermore, students are less likely to demonstrate behaviours that challenge and are at a reduced risk of involvement in crime and violence in the long term.

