Secondary outcomes will be assessed similarly by establishing diagnostic plots to explore the distribution and identify the most appropriate regression approach, including stratification factors and baseline covariates within a multilevel model. These plots include residual plots to check for violations like non-linearity and heteroscedasticity, normal probability plots to assess the normality of residuals, and histograms of residuals to identify potential outliers.

Outcomes at the individual level (CYP and school staff) will be analysed using multilevel modelling, while outcomes at the school level will be done through linear regression. Table 5 sets out the statistical analysis for each outcome by level.

Table 5 Statistical analysis by outcome and level

Outcome	Level	Model	Covariates
Primary outcome Externalising behaviour	CYP	Multilevel model	Pre-treatment scores of outcomes at CYP level

¹⁰ This refers to the binary variable indicating whether the school is above or below the median proportion of FSM6 students

Secondary outcomes Internalising behaviour Non-psychotic psychological distress Well-being Sense of connectedness Exclusions, suspensions and attendance at individual (CYP) level			Demographic factors (sex, FSM status) at CYP level
Secondary outcomes Attitudes related to TIC Well-being	School Staff	Multilevel model	Pre-treatment scores of outcomes at staff level
Secondary outcomes Staff retention Staff sickness Exclusions & suspensions of CYP School attendance of CYP	School	Linear regression (OLS)	Pre-treatment scores of outcomes at the school level

The syntax in Stata© would be as below, using the ‘mixed’ command:

```
Full adjusted model: mixed post-treatment_outcome TISUK baseline_outcome fsm || school_id
```

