2.3.2 Secondary outcome analysis

The remaining secondary outcomes at the pupil and school staff levels follow the same equation as above. Secondary outcomes measured at the school level will be estimated using linear regression (ordinary least squares, OLS) with robust standard errors to account for potential heteroscedasticity. Since there is only one observation per school for school-level outcomes, clustering at the school level is not applicable, and robust standard errors are used to ensure valid statistical inferences in the presence of heteroscedasticity.

The **school-level model** is a linear regression set out by:

$$Z_j = \gamma_0 + \gamma_1 Intervention_j + \gamma_2 BaseS_j + \gamma_3 FSM_j + \mu_j$$
$$\mu_j \sim N(0, \sigma_\mu^2)$$

Where:

- Z_j is the outcome at the school level;
- γ_0 is the intercept;
- *Intervention* is a binary variable that equals 1 if school is within intervention arm and 0 otherwise;
- $BaseS_j$ represents the baseline covariate at the school level, which is centred around the grand mean of the school level;
- FSM_j is a binary variable indicating whether a school's % proportion of FSM pupils is above or below the median in the sample of schools participating in the trial;
- μ_j is the random error across all school
- σ_μ^2 is the residual/error variance between schools

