2.3.10 Intra-cluster correlations (ICCs)

In this trial, the units forming clusters are schools. The Intraclass Correlation Coefficients (ICCs) will be computed for the baseline measure of the primary outcome, externalising behaviour, using an empty multilevel model without covariates. The ICC will be estimated at the school level, as this is the clustering level in the study design.

Specifically, a two-level random intercept model will be fitted, with children and young people (CYP) at level 1 nested within schools at level 2. The ICC will be calculated using the following formula:

$$ICC = \frac{\sigma_{School}^2}{(\sigma_{School}^2 + \sigma_{CYP}^2)}$$

Where σ_{School}^2 is the variance at the school level, and σ_{CYP}^2 is the variance at the CYP level.

The 'estat icc' command within Stata© 17 will be used to obtain the ICC estimate and its corresponding confidence interval from the empty multilevel model¹³.

¹³ This has already been estimated on baseline data

Additionally, the ICC will be estimated from the primary analysis model, which includes covariates and other predictors, to assess the impact of adjusting for these variables on the clustering effect.

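### Network consultancy groups intervention schools in twos and threes while the planned models treat schools as independent: intervals will be too narrow if the effect varies between networks, so record network membership and pre-specify a group-aware analysis

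*Protocol*

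**What the plan says.** **Delivery.** Protocol 2.3, item 3, states: "Schools will be provided with three consultancy support meetings from an experienced educational consultant at TISUK with each one involving two to three schools". Part of the stated purpose is that schools support one another and exchange practice. Item 1 says of whole-staff training: "The sessions will be conducted virtually, potentially accommodating multiple schools in each training session". Item 2 says of senior leadership training: "The training will be conducted in cohorts across the project schools, with SLT members from each school attending the training at different times". Control schools continue business as usual (SAP 2.1), so any delivery grouping exists in one arm only.

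**Analysis.** The SAP treats the school as the only cluster:
- SAP 2.3.10: "In this trial, the units forming clusters are schools".
- SAP 2.3, Stata syntax for pupil outcomes: "Full adjusted model: mixed post-treatment_outcome TISUK baseline_outcome fsm || school_id". SAP 2.3.2 applies the same equation to staff outcomes.
- SAP 2.3.2, on the OLS model: "Since there is only one observation per school for school-level outcomes, clustering at the school level is not applicable". Its standard errors are robust to heteroscedasticity only.
- SAP 2.2: the MDES formula has a school term and a pupil term and nothing above the school.

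Neither document contains a network, consultant or cohort term, or a sensitivity analysis for one.

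**The concern.** This is a partially nested design: schools are grouped by delivery in the intervention arm and ungrouped in the control arm. If one network works better than another, its two or three schools move together. A school-only model treats that shared movement as two or three independent pieces of evidence, so it understates the variance of the intervention-arm mean.

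The route is plausible here. SAP 2.3.9 says that pupils are affected through changes in school policies and procedures, and network consultancy is the component meant to help leaders embed those changes. The ICC of 0.015 behind the SAP's MDES of 0.094 is a baseline estimate (SAP 2.3.10, footnote 13). It predates delivery and cannot contain variation that delivery creates.

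At stake is the coverage of the intervals for the primary, staff and school-level effects.

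**Working it through.** **Inputs.** From SAP Table 4: 40 intervention and 38 control schools, 166 pupils per school, ICC 0.015, two-sided alpha 0.05, power 0.8. From Protocol 2.3: two to three schools per consultancy meeting. Not in the documents, so assumed: the SD of the effect between networks, s = 0.05 to 0.10 (25% to 50% of the 0.2 target effect), and 16 stable networks, eight of two schools and eight of three (8×2 + 8×3 = 40).

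**Step 1: the plan's own figures.** With 100 schools, 160 pupils and ICC 0.03, the two-level formula with normal quantiles gives 0.1064, exactly as stated. For the randomised sample:
- Variance of a school mean: v = 0.015 + 0.985/166 = 0.02093.
- SE = √[0.02093 × (1/40 + 1/38)] = √(0.02093 × 0.05132) = 0.0328.
- MDES = 2.838 × 0.0328 = 0.093, where 2.838 is the t multiplier on 76 df. The SAP states 0.094.

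Both stated figures are therefore what one obtains with independent schools.

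**Step 2: true SE with network variation.** The intervention-arm mean gains s² × Σg²/40², where Σg² = 8×4 + 8×9 = 104, that is 0.065 s².
- s = 0.05: √(0.001074 + 0.000163) = 0.0352.
- s = 0.10: √(0.001074 + 0.000650) = 0.0415.

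**Step 3: SE the school-only model reports.** Part of the network variation enters the between-school residual. The intervention-arm sample variance rises by s² × (40 − 104/40)/39, so the pooled variance rises by s² × 37.4/76 = 0.492 s².
- s = 0.05: √[(0.02093 + 0.00123) × 0.05132] = 0.0337.
- s = 0.10: √[(0.02093 + 0.00492) × 0.05132] = 0.0364.

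**Step 4: result.** Coverage is from simulation of school means, 40,000 runs per cell.

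| Network SD | True SE | Model SE | Ratio | 95% interval covers |
|---|---|---|---|---|
| 0 | 0.0328 | 0.0328 | 1.00 | 95% |
| 0.05 | 0.0352 | 0.0337 | 1.04 | about 94% |
| 0.10 | 0.0415 | 0.0364 | 1.14 | about 91% |

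A network-clustered SE with Satterthwaite df brings coverage back to about 95% in each row. Errors that allow only unequal variances do not: at s = 0.10 the model variance becomes (0.02093 + 0.00959)/40 + 0.02093/38 = 0.00131, SE 0.0362, ratio 1.15.

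If the baseline score explained 50% of school and 40% of pupil variance (assumed, since the SAP lists these correlations as n/a), the ratios would be 1.08 to 1.22 and coverage about 93% to 89%.

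**Step 5: second parameterisation.** Hold total school variance fixed and let a share r of it be common to a network of g schools. The variance of an intervention school mean becomes v + (g − 1) × r × 0.015. For g = 2 to 3, the SE ratio is 1.02–1.03 at r = 0.1, 1.05–1.10 at r = 0.3 and 1.08–1.16 at r = 0.5. For the school-level OLS, the ratio √{[(1 + (g − 1)r)/40 + 1/38] / (1/40 + 1/38)} is 1.02–1.05, 1.07–1.14 and 1.12–1.22 at the same values of r.

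**Step 6: MDES.** Using the full true SE at s = 0.10, 2.838 × 0.0415 = 0.118, below 0.20.

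**The case against.** **Schools were randomised, so a school-level analysis is the natural one.** This stands in part. If TISUK has no effect in any school, grouping adds no correlation and the planned test is valid. A reader might infer that the false-positive rate is inflated. The documents do not support that for the hypothesis of no effect anywhere; the problem arises only when effects exist and differ between networks.

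**No between-network variance is given.** This stands. A reader might conclude that the intervals are too narrow as a matter of fact, but that conclusion is conditional. An SD of 0.10 is also generous: its variance, 0.01, is two-thirds of the whole baseline between-school variance of 0.015.

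**The grouping is looser than a clean hierarchy.** This stands. Protocol 2.3 does not say that the same schools meet each time. The case-study plan in Protocol 5.2 expects two network consultants per school, so a single shared consultant is not established. Training cohorts might look like the larger problem, but sharing of whole-staff sessions is only a possibility, staff of one school may join different cohorts, and missed days may be made up on courses outside the project (Protocol 2.3 and Table 8). Cohorts are therefore crossed with schools and are the weaker route. Larger stable groups, such as five schools per consultant, would do more damage, but nothing in the text describes them.

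**The MDES effect is easily overstated.** This stands. Setting 0.118 against 0.094 compares a world with network variation to one without it. The part the planned model misses at SD 0.10 is about 14%, that is 0.094 × 1.14 = 0.107.

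**A group model as primary would rest on an imprecise variance from about 16 groups.** This stands, and is why the planned model should remain primary. It does not argue against a pre-specified companion analysis.

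**Conclusion.** The point holds in conditional form. The delivery model creates groups of two to three intervention schools, and the planned pupil, staff and school-level models and the MDES ignore them. If the effect varies between networks with an SD of 0.05 to 0.10, the model SE is too small by a factor of about 1.04 to 1.14 and 95% intervals cover about 94% to 91%. If the effect does not vary, the planned intervals are right. These figures assume stable networks with all 40 intervention schools placed in one; four of those schools dropped out after randomisation (SAP 2.2).

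Two stronger readings are not supported. The trial does not become underpowered, because the MDES stays below 0.20 throughout. Nor can it be said that every model ignores the grouping: the CACE analysis in SAP 2.3.9 clusters its standard errors at a level it does not name.

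This is a cheap improvement to interval validity. It does not invalidate the primary analysis.

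**What to change.** 1. **Data.** Ask TISUK for a network-consultancy group ID for each intervention school, alongside the attendance data it already provides (Protocol Table 7). Give each control school its own ID, and likewise any intervention school that dropped out before joining a network, so that all randomised schools stay in the analysis. If networks change between meetings, use the group attended most often.
2. **SAP 2.3 and 2.3.1.** Keep the school-only model as primary. Before outcome data are seen, pre-specify a group-aware analysis reported beside it for the primary and staff outcomes. Either add a network effect in the intervention arm only (for example `|| netgroup: TISUK, nocons || school_id:`) or cluster the standard errors on network, with small-sample degrees of freedom.
3. **SAP 2.3.2.** Use network-clustered errors for the school-level OLS.
4. **SAP 2.3.10 and 2.3.9.** Acknowledge delivery groups as a second source of clustering, and name the clustering level for the CACE.

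The cost is one ID column, a few lines of SAP text, a slightly wider interval and an imprecise network variance that may be estimated at zero. In that case the mixed model returns the planned result. Specifying this now matters, because the same analysis added after results are known would look selective.
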